11.1 Demographic and Vital Signs

Demographic variables collected in this study include age in years (at time of screening), sex, race, ethnicity, body mass index (BMI), weight, height, iris color, and study eye (OD or OS). Subjects who record more than one race will be grouped into a single category denoted as 'Multiple Race'.

Age (years) will be summarized using continuous descriptive statistics. Age will also be categorized as follows: <65 years and ≥65 years.

The number and percentage of subjects will be presented for age category, sex, race, ethnicity, iris color and study eye (OD or OS). Percentages will be based on the total number of subjects in the ITT set. A subject listing that includes all demographic variables will be provided.

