13.2 Treatment Exposure

Extent of exposure will be calculated in days using the following:

Extent of Exposure (days) = [Date of last dose – Date of first dose] + 1

Extent of treatment exposure (days) and the total number of doses received for each subject exposed to IMP will be summarized with continuous descriptive statistics using the Safety set. A subject listing of treatment exposure will also be produced.

14. Analysis of the Primary Endpoint

The primary endpoint is the mean change from baseline (Visit 2 / Day 1) to end of treatment (Visit 8 / Day 43) in BCVA letter score of the study eye as measured by the ETDRS testing method using the Evaluable set. BCVA will be measured at the beginning of every study visit and change from baseline for each subject will be calculated as follow-up visit minus baseline visit. Quantitative summary statistics will be used to summarize the BCVA letter score and change from baseline at each visit. A two-tailed, one-sample t-test will be used to assess the mean change from baseline in BCVA letter score at each visit, in which the change from baseline BCVA letter score will be compared to a reference value of zero. The following SAS code will be used to run the one-sample t-test:

```
PROC TTEST H0=0 ALPHA=0.20 DATA=INDATA;
  VAR BCVA_CHG;
RUN;
```

where

- *INDATA* is the name of the input dataset;
- *BCVA_CHG* is the change in BCVA from baseline to the follow-up visit.

A mixed model accounting for repeated measures will also be used to analyze BCVA. This model will include the change from baseline in BCVA letter score as the response variable and baseline BCVA letter score, smoking status and visit as explanatory variables for adjustment. LS means for each visit will be calculated along with corresponding 95% CIs and p-values. SAS code to implement this repeated measures mixed model is as follows:

```
PROC MIXED DATA=INDATA;
  CLASS SUBJID SMOKE VISIT;
  MODEL CHG = BASELINE SMOKE VISIT / DDFM = KR SOLUTION;
  REPEATED VISIT / SUBJECT=SUBJID TYPE=UN;
  LSMEANS VISIT / CL;
RUN;
```

where

- *INDATA* is the name of the input dataset sorted by *SUBJID* and *VISIT*;
- *SUBJID* is the subject ID number;
- *SMOKE* is the subject's smoking history (Never smoked, Ex-smoker, Currently smokes);

- *VISIT* is the visit at which the BCVA letter score was collected;
- *CHG* is the change from baseline in the BCVA letter score;
- *BASELINE* is the baseline BCVA letter score;

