The Kenward-Roger method will be used to determine denominator degrees of freedom. An unstructured variance-covariance matrix will be used for the above repeated measures model. If the model does not converge using the unstructured matrix, the first order autoregressive structure and the compound symmetry structure will be employed, in that order.

The above analyses will be repeated on the PP set as a sensitivity analysis.

Additionally, the number of subjects with change from baseline in BCVA letter score for the following categories will be summarized with counts and percentages:

- ≥ 15 letters;
- ≥ 14 and ≥ 10 letters;
- ≥ 9 and ≥ 5 letters;
- ≥ 4 and ≥ -4 letters;
- ≥ -5 and ≥ -9 letters;
- ≥ -10 and ≥ -14 letters;
- ≤ -15 letters.

BCVA results will also be presented in a data listing. BCVA results in the fellow eye are not included in the analyses but will be included in the listings. BCVA will also be summarized by visit using box plots.

15. Analysis of the Secondary Endpoints

The analyses for secondary endpoints (incidence, seriousness and severity of AEs) will be discussed in the next section as part of the safety analyses. There is no secondary efficacy endpoint for the study.

16. Safety Analyses

Safety will be assessed for the following endpoints using the Safety set:

- Incidence, seriousness, and severity of AEs;
- Observed slit-lamp biomicroscopy values;
- Observed intraocular pressure (IOP) values;
- Changes from baseline in clinical laboratory values;
- Changes from baseline in physical examination;
- Changes from baseline in vital signs.

Adverse events will be presented using frequencies and percentages of subjects.

Other safety endpoints including slit-lamp biomicroscopy, IOP, clinical laboratory values, physical examination, and vital signs will be summarized using descriptive statistics. Changes or shifts from baseline will also be summarized where appropriate. Assessments performed by eye (study eye and fellow eye) will be summarized separately. No statistical inferential testing will be performed for safety variables.

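### The additional repeated-measures model weights the smoking categories equally, so its single-arm LS means target an unstated population rather than the analysed patients

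*SAP*

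**What the plan says.** SAP Section 14 tests the raw BCVA change against zero with a one-sample t-test at each visit; Visit 8 in the Evaluable set is primary. It then adds: "A mixed model accounting for repeated measures will also be used to analyze BCVA". The model statement is "MODEL CHG = BASELINE SMOKE VISIT / DDFM = KR SOLUTION". `SMOKE` is in the CLASS statement and is defined as "smoking history (Never smoked, Ex-smoker, Currently smokes"). The output is requested with "LSMEANS VISIT / CL", and the text says that "LS means for each visit will be calculated along with corresponding 95% CIs and p-values". On covariance and repetition: "An unstructured variance-covariance matrix will be used for the above repeated measures model" (with fallbacks if it does not converge), and "The above analyses will be repeated on the PP set as a sensitivity analysis".

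SAP Section 3.4 states the hypothesis for the mean change at 6 weeks. SAP Sections 4.1 and 5 describe a single arm. On demographics, SAP Section 11.1 says: "The number and percentage of subjects will be presented for age category, sex, race, ethnicity, iris color and study eye". Smoking is not among the variables listed there or in Section 11.2.

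**The concern.** Unless told otherwise, the SAS LSMEANS statement averages over the levels of every other class effect with equal weights. This is software behaviour, not SAP text, but the SAP's code triggers it. Two current smokers would count as much as fifteen never-smokers. In a two-arm additive model this is harmless, because the same weights enter both arms and cancel in the difference. Here the LS mean is the reported effect and is compared with zero.

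The result describes a population with equal smoking shares. In the text available to me, which lacks SAP Section 8 and the opening of Section 9, nothing states or justifies that target. Since smoking is in no planned summary, a reader who saw the LS mean and the raw mean disagree could not tell whether the weighting was the cause.

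**Working it through.** The plan gives no figure to reproduce: it has no smoking counts, smoking effect, SD or visit correlations.

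**Inputs.** From the SAP: about 25 evaluable subjects (Section 6), three smoking categories, an additive model, and BCVA at Visits 3 to 10, which makes 8 post-baseline visits (Section 4.2). Assumed: all 8 visits enter the model; baseline is balanced over smoking groups; never/ex/current splits of 15/8/2, 12/8/5 and 8/8/9; current smokers change by 4 letters less than the others; data are complete except in the dropout example.

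**Expected shift.** The coded LS mean minus the mean of the analysed patients is Σ(1/3 - p_k)·m_k, where p_k is the share and m_k the mean change of category k. With the assumed deficit this is -4 × (1/3 - n3/25), where n3 is the number of current smokers:

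- 15/8/2: -4 × (0.3333 - 0.08) = -1.01 letters
- 12/8/5: -4 × (0.3333 - 0.20) = -0.53
- 8/8/9: -4 × (0.3333 - 0.36) = +0.11

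If all m_k are equal, the expected shift is zero for any split.

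**Standard error, known covariance.** The squared ratio of SEs (equal over observed weights) at Visit 8 is 1 + (n·k - 1)·v/s², with k = (1/9)(1/n1 + 1/n2 + 1/n3), v = 1/(1'Σ⁻¹1) and s² the Visit 8 variance. At 15/8/2, n·k = 25 × (0.0667 + 0.1250 + 0.5000)/9 = 1.921. With equal variances and compound symmetry 0.7, v/s² = (1 + 7 × 0.7)/8 = 0.7375, so the ratio is √(1 + 0.921 × 0.7375) = 1.296.

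Ranges over compound symmetry 0.5 to 0.9 and AR(1) 0.7 to 0.9:

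| Split | Equal variances | SD rising from 4 (Visit 3) to 8 letters (Visit 10) |
|---|---|---|
| 15/8/2 | 1.19-1.36 | 1.06-1.15 |
| 12/8/5 | 1.03-1.06 | 1.01-1.02 |
| 8/8/9 | 1.00 | 1.00 |
| 20/5 (two categories, 1/2 each) | 1.12-1.23 | 1.04-1.09 |

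**Specified unstructured fit.** Simulated REML fits (1,500 trials per scenario, SEs before the Kenward-Roger adjustment) gave median ratios at 15/8/2 of 1.13-1.25 with equal variances and 1.04-1.10 with rising SD. At 12/8/5 they were 1.02-1.04 and 1.01. With no true smoking effect, the gap between the coded LS mean and the raw mean is pure noise. Its SD over trials was about 0.6-1.4 letters at 15/8/2 and 0.2-0.5 at 12/8/5 (SD of change 6 letters, or rising from 4 to 8).

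**Does observed weighting recover the patients' mean?** In every complete-data fit it returned the raw Visit 8 mean to rounding error. In a separate simulated data set (6 visits, split 12/10/3, assumed category effects +2/+1/-3 letters) the raw mean was 1.288. Observed weights gave 1.288 (SE 1.000) and the coded equal weights gave 0.563 (SE 1.143).

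**Missing visits.** With dropout the SE ratio can fall marginally below 1. It is 0.99 at 10/8/7 when five of the ten leave after Visit 5 (AR(1) 0.7). Weighting by record also differs from weighting by subject. Suppose five subjects with baseline 40 leave after Visit 5 (3 records each) and twenty with baseline 50 stay (8 records each). The mean baseline is (5 × 40 + 20 × 50)/25 = 48.0 per subject but (15 × 40 + 160 × 50)/175 = 49.1 per record.

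**The case against.** The case against is mainly about weight. The code fully determines the estimate, and equal margins are a legitimate standardisation. The model is additional, the 0.20 level in SAP Section 9.4 belongs to the primary analysis, SAP Section 24 names no separate LS-mean table, and the raw mean is reported at every visit, so a gap would be visible. The trial is unpowered and called exploratory. Every magnitude is assumed, and near-equal splits make the effect negligible. With complete data, the remedy only makes the point estimate repeat the raw mean.

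Most of this stands and sets the grade. It does not remove the point. Visible disagreement between two estimates is little help if smoking is not tabulated and the target is not named. Changing the weights alters the estimate, CI and p-value of a planned analysis, so it is more than labelling. Observed weighting also leaves the model its proper use, which is visits with missing data.

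Two further objections are fair. The simulated SEs are not the Kenward-Roger SEs that would be reported. Any use for SAP Section 17.1 endpoints would need endpoint-specific baselines, so it costs more than the BCVA change alone.

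**Conclusion.** The concern holds as a free improvement and does not threaten the primary test. As coded, the per-visit LS means, CIs and p-values refer to equal smoking shares, and no available text says that this is wanted. In expectation they depart from the analysed patients' mean only if smoking is both unbalanced and related to BCVA change: about 1 letter at 15/8/2 and half a letter at 12/8/5 under the assumed 4-letter deficit. Loss of precision needs only imbalance. With complete data it ranges from nothing at 8/8/9 to an SE up to 1.36 times as large at 15/8/2. The mechanism is certain; the size cannot be known from the documents.

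SAP Section 17.1 analyses its quantitative endpoints in a manner similar to the primary one without saying whether this model is included. If it is, the point carries over to CST and the fluid and PED heights, but not to the FP/FA sizes, which have one post-baseline visit.

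**What to change.** - Add `OM=<data set>` and `E` to the LSMEANS options. The data set should have one row per analysed subject at each visit, with that subject's `SMOKE` and `BASELINE`. This weights smoking by subject and holds baseline at its mean over analysed subjects even when visits are missing. I have not run it in SAS; `E` prints the coefficients, so both can be confirmed. With complete data, each LS mean must equal the raw mean change at that visit.
- Add one sentence to SAP Section 14 saying that LS means are weighted to the observed smoking distribution of the analysed set (Evaluable or PP). If equal shares are intended, state that and the reason.
- Add smoking counts to Table 14.1.2.
- Say whether SAP Section 17.1 uses this model. If so, apply the same weighting to endpoints with repeated post-baseline visits, each with its own baseline.

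For BCVA the cost is one small data set per analysis set, a short code change, one sentence and one table row. Each Section 17.1 endpoint would add its own baseline column and call. No new data are needed, since the model already requires smoking status.

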- Presence of Hemorrhage in the PED (including area of the hemorrhage) as measured by FP/FA
- Presence of Disciform Scar/Retinal Fibrosis as measured by FP/FA

18. Interim Analyses

Continuous data monitoring will be performed. One interim analysis will be performed when two-thirds of all entered subjects have reached Day 15 (Visit 4). The interim analysis will include only a subset of the secondary endpoint (i.e., accumulated AE information).

Recruitment into the trial will be stopped if the interim analysis shows relevant safety problems with ALK4290. No formal futility analysis will be conducted.

19. Pharmacokinetic Analysis

A separate PK plan will be created to describe details pertinent to the analysis of collected PK data.

20. Biomarker Analysis

A separate biomarker plan will be created to describe details pertinent to the exploratory analysis of collected biomarker data.

21. Changes from Protocol-Stated Analyses

Not applicable.

22. References

Not applicable.

23. Revision History

Documentation of revision to the SAP will commence after approval of the Final version 1.0.

24. Tables

Tables that will be included in the topline delivery are shown in boldface font and the tables, listings, and figures for the interim analyses are italicized.

Table Number	Title	Set
14.1.1	Subject Disposition	All Patients
14.1.2	Demographics and Baseline Characteristics	ITT Set
14.1.3.1	Ocular Medical History	ITT Set
14.1.3.2	Non-Ocular Medical History	ITT Set
14.1.4.1	Ocular Concomitant Medications	ITT Set
14.1.4.2	Non-Ocular Concomitant Medications	ITT Set
14.1.5	Compliance with Study Drug	Safety Set
14.1.6	Exposure to Study Drug	Safety Set
Primary and Exploratory Efficacy Analyses		
14.2.1.1	Summary of Study Eye BCVA Letter Score and Change from Baseline at Scheduled Visits	Evaluable Set
14.2.1.2	Summary of Study Eye BCVA Letter Score and Change from Baseline at Scheduled Visits	PP Set
14.2.1.3	Categorical Summary of Study Eye BCVA Letter Score Change from Baseline at Scheduled Visits	Evaluable Set
14.2.2.1	Summary of Study Eye Central Subfield Thickness (µm) and Change from Baseline as Measured by SD-OCT at Scheduled Visits	Evaluable Set
14.2.2.2	Summary of Study Eye Central Subfield Thickness (µm) and Change from Baseline as Measured by SD-OCT at Scheduled Visits	PP Set

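### Five of the seven BCVA change categories in SAP section 14 use the wrong inequality: as written, the table counts gainers two to six times and omits losses of 11 to 14 letters

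*SAP*

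**What the plan says.** SAP section 14 defines the sign of the change: "change from baseline for each subject will be calculated as follow-up visit minus baseline visit". A gain is therefore positive and a loss negative. After the t-test and the mixed model it adds a categorical summary, in which "the number of subjects with change from baseline in BCVA letter score for the following categories will be summarized with counts and percentages". Seven rows follow. The first is a change of at least 15 letters and the last is a change of -15 or lower. The five between them are:

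- Row 2: "≥ 14 and ≥ 10 letters"
- Row 3: "≥ 9 and ≥ 5 letters"
- Row 4: "≥ 4 and ≥ -4 letters"
- Row 5: "≥ -5 and ≥ -9 letters"
- Row 6: "≥ -10 and ≥ -14 letters"

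SAP section 24 lists the output as Table 14.2.1.3, "Categorical Summary of Study Eye BCVA Letter Score Change from Baseline at Scheduled Visits", for the Evaluable Set. It gives a title only. The protocol defines no such categories, SAP section 21 records no change from the protocol's analyses, and SAP section 1 says the SAP's methods take precedence over the protocol's. The list in section 14 is therefore the only specification of this table.

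**The concern.** When two lower limits are joined by *and*, only the higher one has any effect. Rows 2 to 6 therefore have no upper limit, and they overlap one another and row 1. The rows labelled as moderate losses admit subjects who are stable or have gained, while some subjects with real losses are left out of the table.

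The study has one arm and is stated not to be powered, so description carries much of the interpretation. Protocol section 10.4.1 singles out the spread of within-subject BCVA changes around zero as being of particular interest, and Table 14.2.1.3 is the only listed table that bins those changes. Coded as specified, it would put most subjects in the loss rows under any plausible distribution. It would do so at each of the eight post-baseline visits with a visual acuity test (Visits 3 to 10).

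**Working it through.** **Inputs.** The seven rows and the direction of change come from SAP section 14. Letter-score changes are whole numbers. The plan states no expected percentage for any row, so there is no figure of its own to reproduce.

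**Step 1: reduce each row.** For a > b, the condition (x ≥ a and x ≥ b) is the same as x ≥ a. The rows become ≥15, ≥14, ≥9, ≥4, ≥-5, ≥-10 and ≤-15.

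**Step 2: assign every whole-letter change to all the rows it satisfies.**

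| Change (letters) | Rows matched as written | Number of rows | Intended row |
|---|---|---|---|
| ≥15 | 1 to 6 | 6 | 1 |
| 14 | 2 to 6 | 5 | 2 |
| 10 to 13 | 3 to 6 | 4 | 2 |
| 9 | 3 to 6 | 4 | 3 |
| 5 to 8 | 4 to 6 | 3 | 3 |
| 4 | 4 to 6 | 3 | 4 |
| -4 to 3 | 5, 6 | 2 | 4 |
| -5 | 5, 6 | 2 | 5 |
| -6 to -9 | 6 | 1 | 5 |
| -10 | 6 | 1 | 6 |
| -11 to -14 | none | 0 | 6 |
| ≤-15 | 7 | 1 | 7 |

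Every gain is counted at least twice. Gains of 10 to 13 and of 5 to 8 miss their own rows. Changes of -4 to 3 miss the stable row and enter both loss rows. Losses of 6 to 9 are moved into the next worse row. Losses of 11 to 14 disappear.

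**Step 3: illustrate the size.** The documents give neither a mean nor an SD for the change. Assume changes that are normal with mean μ and SD σ, rounded to whole letters. A row that reduces to ≥ a then holds 1 − Φ((a − 0.5 − μ)/σ), and a band from b to a holds Φ((a + 0.5 − μ)/σ) − Φ((b − 0.5 − μ)/σ). With μ = 0 and σ = 8:

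- Row 6 as written: 1 − Φ(−10.5/8) = 90.5%.
- Row 6 as intended (-14 to -10): Φ(−9.5/8) − Φ(−14.5/8) = 8.3%.
- In no row (-14 to -11): Φ(−10.5/8) − Φ(−14.5/8) = 6.0%.

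| Row | As written means | As written, % | Intended band | Intended, % |
|---|---|---|---|---|
| 1 | ≥15 | 3.5 | ≥15 | 3.5 |
| 2 | ≥14 | 4.6 | 10 to 14 | 8.3 |
| 3 | ≥9 | 14.4 | 5 to 9 | 16.9 |
| 4 | ≥4 | 33.1 | -4 to 4 | 42.6 |
| 5 | ≥-5 | 75.4 | -9 to -5 | 16.9 |
| 6 | ≥-10 | 90.5 | -14 to -10 | 8.3 |
| 7 | ≤-15 | 3.5 | ≤-15 | 3.5 |
| Sum | | 225.0 | | 100.0 |

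Row 6 is overstated 90.5/8.3 = 10.9-fold. With the planned 25 or so evaluable subjects, row 6 would show about 0.905 × 25 = 22.6 subjects instead of 0.083 × 25 = 2.1. Row 5 would show 0.754 × 25 = 18.9 instead of 0.169 × 25 = 4.2. About 0.060 × 25 = 1.5 subjects would be missing.

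**Step 4: vary the assumptions.** At mean 0, SDs of 6 to 10 give sums of 216.6% to 235.8%. Over means of -2, 0, 2 and 5 combined with SDs of 5, 8 and 10:

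- The sum runs from 187.5% to 311.0%.
- Row 5 shows 63.7% to 98.2%, against an intended 2.7% to 24.2%.
- Row 6 shows 80.2% to 99.9%, against an intended 0.2% to 12.1%.
- The share in no row runs from 0.1% to 9.2%.

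**Step 5: check the correction.** With ≤ as the first sign in rows 2 to 6, every integer from -100 to +100 falls in exactly one row.

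**The case against.** The best reply is that this is a typographical slip with an obvious remedy. The paired end points form adjoining whole-number bands between the two open-ended rows, and only one partition fits them. Percentages totalling about 200% or more would be noticed, and a competent programmer would repair the signs. The table is a descriptive addition. Change from baseline is also summarised at each visit with SD, median, minimum and maximum (Tables 14.2.1.1 and 14.2.1.2), letter scores have box plots and a subject listing, and losses of more than 15 letters are reported separately as events of special interest (Table 14.3.5). The text was also read from a PDF by a program, so a misread symbol cannot be ruled out completely.

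Much of this stands as a limit on the consequences. The intent is clear, no inference is touched, and the listing would allow any miscount to be recovered. It does not remove the error. A silent repair would leave the delivered table different from the governing SAP with no record of why. The other summaries do not show how many subjects gained or lost by band, and the special-interest events cover only the extreme losses. A reading error is unlikely, because the last row of the same list prints ≤ correctly and all five two-sided rows show the same fault. Only a look at the source file can settle that.

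**Conclusion.** The concern holds. As printed, five of the seven rows are wrong, and following them gives a wrong table. The overlaps and the omission of losses of 11 to 14 letters follow from the wording alone. The percentages, such as a 225% total and 90.5% against 8.3% in row 6, rest on an assumed normal change with mean 0 and SD 8. The direction and rough scale persist over the range of means and SDs tried. The error is confined to the categorical summary. The one-sample t-test, the mixed model, the significance level and the sample size are unaffected. It should be corrected before the table is programmed.

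**What to change.** In SAP section 14, change the first sign in rows 2 to 6 from ≥ to ≤, so that the categories read:

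- ≥ 15
- ≤ 14 and ≥ 10
- ≤ 9 and ≥ 5
- ≤ 4 and ≥ -4
- ≤ -5 and ≥ -9
- ≤ -10 and ≥ -14
- ≤ -15

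Make the same change in any shell and program for Table 14.2.1.3, and add a programming check that the row counts at each visit sum to the number of subjects with a non-missing change. The cost is five symbols and a line in the SAP revision history. No data collection, inferential analysis or sample size changes.

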16.1 Adverse Events

AEs are defined as any untoward medical occurrence associated with the use of an IMP in humans, whether or not considered IMP-related. All AEs, serious and non-serious, occurring during the course of the clinical trial (i.e., from signing the informed consent through the follow-up period) will be collected, documented, and reported. All AEs that occur or worsen on or after the first use of IMP will be considered as treatment-emergent AEs (TEAE). Reported AEs that begin prior to the first dose of IMP are classified as non-TEAEs; these will only be included in subject listings and not included in summary tables.

When reporting an AE, the event description should use the best matching terminology describing the event as found in the Common Terminology Criteria for Adverse Events (CTCAE v4.03). Standardized terms from the CTCAE will be used to categorize events for reporting to regulatory authorities using the Medical Dictionary for Regulatory Activities (MedDRA, v. 21.0).

The severity of all reported AEs are graded by the investigator into one of the following five (5) CTCAE categories:

- Grade 1 (Mild)
- Grade 2 (Moderate)
- Grade 3 (Severe)
- Grade 4 (Life-Threatening)
- Grade 5 (Death)

The relatedness of IMP to AE will be classified as definite, possibly, or unrelated. Documentation of AEs will include start date, end date, seriousness, severity, relatedness, whether or not medication was required, outcome, and action taken with the study agent.

A serious adverse event (SAE) is defined for this protocol as any AE that meets one or more of the following criteria:

- A death (CTCAE Grade 5 event) occurring during the study, whether or not considered treatment-related;
- A life-threatening event (CTCAE Grade 4);

- An event requiring inpatient hospitalization or prolonged hospitalization due to the adverse event;
- An adverse event resulting in a significant, persistent, or permanent change, impairment, damage or disruption in the participant's body function or structure, physical activities or quality of life;
- An event that otherwise required a medical or surgical intervention to preclude permanent impairment or damage (excluding unrelated elective or cosmetic procedures).

An AE of special interest (AESI) is defined for this protocol as any the following outcomes:

- Hepatic injury defined by the following alterations of liver parameters:
 - For subjects with normal liver function at baseline an elevation of aspartate aminotransferase (AST) and/or alanine aminotransferase (ALT) ≥ 3 -fold the upper limit of normal (ULN) combined with an elevation of total bilirubin ≥ 2 -fold the ULN measured in the same blood draw sample;
- Abrupt decrease of BCVA (> 15 letters lost from baseline);
- QTc interval prolongation ($> +50$ ms from baseline and > 450 ms).

An overall tabular summary of TEAEs will be presented that includes the number and percentage of subjects who experienced at least one TEAE. These summaries will also include breakdowns of TEAEs further categorized as ocular or non-ocular, and within these categories as drug-related TEAEs, TEAEs with CTCAE Grade 3/4/5, drug-related TEAEs with CTCAE Grade 3/4/5, TEAEs with an outcome of death, serious TEAEs, drug-related serious TEAEs, TEAEs leading to discontinuation of IMP and drug-related TEAEs leading to discontinuation of IMP.

Furthermore, the number and percentage of subjects with TEAEs by SOC and PT; by SOC, PT and maximal severity; by SOC and PT for TEAEs; by SOC and PT for SAEs; and by SOC and PT for TEAEs leading to subject withdrawal will be presented. Separate summaries will be provided for ocular and non-ocular TEAEs (including systemic). Adverse events of special interest will also be summarized by SOC and PT. These summaries by SOC and PT will be at the subject level. If a subject reports the same PT multiple times within the same SOC, that PT will only be counted once within that SOC. As with the PT, if a subject reports multiple conditions within the same SOC, that SOC will only be counted once.

All AEs (including non-TEAEs) will also be presented in subject listings.

